8.3.6 PK BLOOD SAMPLES

Blood samples for plasma concentration analysis will be collected during the study for a population PK evaluation of XEN1101. The dates and times of the last dose of background AED(s) and study drug intake, and the blood sample collection dates and times will be recorded on the eCRF. A subset of up to 40 patients may be requested to provide additional PK samples after providing informed consent to more fully define the PK profile of XEN1101.

A separate population PK analysis plan will be generated to support the population PK analysis in focal epilepsy patients. The population PK will be characterized by nonlinear mixed-effects modeling. A separate report to the clinical study report will be written to cover the population PK analysis.

The relationship between XEN1101 plasma concentration and QTcF, predefined efficacy, and AEs will be investigated in a population PK/PD exposure-response analysis. A separate report to the clinical study report will be written to cover the PK/PD analysis.

Plasma PK samples may also be used for other tests, such as profiling of drug binding proteins, bioanalytical method validation purposes, stability assessments, metabolite assessments, and/or to assess other actions of XEN1101 with plasma constituents. Assessment of the plasma levels of background AEDs and potential changes with co-administration of XEN1101 may also be investigated.

8.3.7 COLUMBIA-SUICIDE SEVERITY RATING SCALE

Patients will undergo assessment by a trained healthcare professional using the C-SSRS “Baseline/Screening” and “Since Last Visit” questionnaires at each visit as described in [Table 1a](#)

and **Table 1b** Schedule of Assessments. Further details of the assessment will be included in the Study Operations Manual. The medical monitor should be notified if a patient reports suicidality.

Details about the C-SSRS assessments ([Posner et al., 2011](https://cssrs.columbia.edu/)), which will be incorporated into the study eCRF, can be found at the following link: <http://cssrs.columbia.edu/>.

8.3.8 BLOOD COLLECTION FOR GENOTYPE/BIOMARKER ASSESSMENT

A blood sample will be collected from each patient who provided informed consent for genotype/biomarker assessments during this study.

Pharmacogenomics Testing

Pharmacogenomic assessment, if conducted, could include potential analysis of the association of both known and unknown DNA and RNA genetic variations with clinical observations (PK, safety, efficacy, or other effects) in the study.

Biomarkers

Biomarkers are defined as biological substances that monitor physiological effects, assess drug activity, and predict clinical outcome, safety and response to therapy.

The collected samples may be stored for up to 10 years after the last visit in the study at a bioanalytical laboratory selected by the sponsor and then destroyed. Samples will only be used for investigations related to disease and/or response to the IMP or related investigational products.

Refer to the Study Laboratory Manual for sample collection, handling, shipping, and storage instructions.

8.4 ADVERSE EVENTS AND SERIOUS ADVERSE EVENTS

8.4.1 DEFINITION OF ADVERSE EVENTS

An AE is any unfavourable and unintended sign (including a new clinically significant abnormal laboratory finding), symptom, or disease temporally associated with the use of a medicinal product, whether or not considered related to it.

An AE may be:

- A new symptom or medical condition.
- A new diagnosis.
- An inter-current illness or an accident.
- A worsening of a medical condition/diseases existing before the start of the clinical trial.
- The recurrence of a disease.
- An increase in frequency or intensity of episodic diseases.
- A clinically significant change in a laboratory or other clinical test parameter that is considered to be an AE by the investigator or sponsor.

An AE does not necessarily include the following:

- An abnormal test that needs repeating, in the absence of accompanying symptoms, and/or any requirement for additional diagnostic testing or medical/surgical intervention. Any abnormal test result that is determined to be an error does not require reporting as an AE.

- Recurrence of the patient's normal seizures are not considered an AE; however, occurrence of status epilepticus or other seizures requiring hospitalization will be counted as an SAE.

Surgical procedures themselves are not AEs; they are therapeutic measures for conditions that require surgery. The condition for which the surgery is required may be an AE. Planned surgical measures permitted by the clinical trial protocol and the condition(s) leading to these measures are not AEs, if the condition leading to the measure was present before inclusion in the trial and has not worsened. In the latter case, the condition should be reported as medical history.

8.4.2 DEFINITION OF SERIOUS ADVERSE EVENTS

An SAE is defined as any AE that fulfils any of the following criteria:

- Results in death.
- Is life-threatening (the term "life-threatening" in the definition of "serious" refers to an event in which the patient was at immediate risk of death at the time of the event; it does not refer to an event which hypothetically might have caused death if it was more severe).
- Requires hospitalization or prolongs existing hospitalization.
- Results in persistent or significant disability/incapacity.
- Is a congenital abnormality/birth defect.
- Is considered medically important (medical and scientific judgment should be exercised in deciding whether other AEs are to be considered serious, such as important medical events that may not be immediately life-threatening or result in death or hospitalization but may jeopardize the patient or may require intervention to prevent one of the other outcomes listed in the definition above. Examples of such events are intensive treatment in an emergency room or at home for allergic bronchospasm; blood dyscrasias; development of drug dependency or drug abuse).

8.4.3 CLASSIFICATION OF AN ADVERSE EVENT

8.4.3.1 SEVERITY OF EVENT

The investigator will also assess the severity (intensity) of each AE as mild, moderate, or severe.

- Mild: Events that are easily tolerated, require minimal or no treatment and do not interfere with the patient's usual daily activities.
- Moderate: Events that are sufficiently discomforting to interfere with patient's usual daily activities.
- Severe: Events that are usually incapacitating with inability to work or perform normal daily activities, or potentially life-threatening. Of note, the term "severe" does not necessarily equate to "serious".
- Life-threatening: Immediate risk of death; significant medical intervention/therapy required; extreme limitation in activity and significant assistance required; hospitalization or hospice care probable.
- Fatal: Death related to SAE.

8.4.3.2 CAUSAL RELATIONSHIP TO STUDY INTERVENTION

The causality assessment of an AE to the IMP will be rated as follows by the investigator:

- Definitely related: A clinical event, including laboratory test abnormality, occurring in a plausible time relationship to the IMP administration, and which cannot be explained by concurrent disease or other drugs or chemicals. The response to withdrawal of the drug should be clinically plausible.
- Possibly related: A clinical event, including laboratory test abnormality, with a reasonable time sequence to the IMP administration, but which could also be explained by concurrent disease or other drugs or chemicals. Information on the drug withdrawal may be lacking or unclear.
- Unlikely related: A clinical event, including laboratory test abnormality, with little or no temporal relationship to IMP administration, and which other drugs, chemicals, or underlying disease provide plausible explanations.
- Not related: A clinical event, including laboratory test abnormality that has no temporal relationship to the IMP or has more likely alternative etiology.

The investigator should also comment on the AE page of the eCRF whether an AE is not related to the IMP, but is related to study participation (eg, study procedures).

8.4.3.3 EXPECTEDNESS

The expectedness of an adverse reaction is determined by the sponsor. An adverse reaction, the nature or severity or frequency of which is not consistent with the applicable reference safety information is unexpected. Reports that add significant information on the specificity, increase in the occurrence or severity of a known and already documented serious adverse reaction are unexpected events. This assessment should be done from the perspective of events previously observed, not on the basis of what might be anticipated from the pharmacological properties of a medicinal product.

For this protocol, the reference document for the assessment of expectedness is the Investigator's Brochure for XEN1101.

8.4.4 TIME PERIOD AND FREQUENCY FOR EVENT ASSESSMENT AND FOLLOW-UP

All (serious and non-serious) AEs detected by the investigator or spontaneously reported by the patient at each visit/examination must be reported in the source and eCRF.

The following information should be reported for each AE, whether or not it can be attributed to the IMP:

- Description of AE.
- Date of onset and date of resolution.
- Characteristics of the event (seriousness, intensity).
- Actions taken (treatment required or dose adjustments must be reported in the eCRF).
- Outcome.
- Relationship with the IMP (causality assessment) and/or study participation.

All AEs must be documented and followed up until the event is either resolved, the condition stabilizes, a satisfactory alternative explanation is found, or the investigator considers it medically justifiable to

terminate the follow-up. The reason(s) will be recorded in the source documents when the AE follow-up is terminated.

The investigator is responsible for following AEs, SAEs and events that caused the patient to discontinue before completing the study, through an appropriate healthcare option. The patient should be followed until the event has resolved or is otherwise explained. Frequency of follow-up evaluation is left to the discretion of the investigator.

8.4.4.1 ADVERSE EVENT REPORTING

All AEs occurring from screening (after signing of the ICF) until 42 days following the last administration of IMP must be recorded in the source document and eCRF in a timely fashion.

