J: Assessments to be completed prior to administration of the first dose of study drug. Patients who do not meet enrollment criteria should not undergo any of the Day 0 tests or assessments other than the required eligibility checks and recording of AEs. Day 0 can start up to 66 days from start of baseline (eligibility for randomization is generally based on the initial 56 days of eDiary entries in the baseline period– Note: In cases where restrictions to site access caused by the COVID-19 pandemic prevent patients from attending site visits, the duration of the baseline may be extended and randomization delayed up to 20 weeks (140 days) from the start of data capture. In cases of delayed randomization, data obtained during the 56 days of eDiary entries prior to randomization will be used to define the “baseline period”, for purposes of determining eligibility for randomization.

K: Patients who stop taking the study drug early should complete all post-treatment follow-up assessments within 7 ± 3 days (Visit F1a) and 42 ± 7 days (Visit F2a) after the last administration of study drug. For patients that complete the DBP but do not enter the OLE, the follow-up (F1a and F2a) visits will occur on the study days shown (63 ± 3 and 98 ± 7).

L: Patients who discontinue early from the study should have all ET evaluations performed on the last day of receiving study drug, or as soon as possible thereafter.

M: Assessment does not need to be repeated if it was normal at screening (or unchanged) and the assessment was completed ≤ 3 days of the baseline visit.

N: Visits 4 and 7 will be conducted as telephone calls to the patient from investigator or designee.

AED = Antiepileptic drug; AUA = American Urological Association; BMI = Body mass index; CBC = Complete blood count; C-SSRS = Columbia-Suicide Severity Rating Scale; DBP = Double-blind period; eCRF = Electronic case report form; eDiary = Electronic diary; ET = Early Termination; FSH = Follicle-stimulating hormone; OLE = Open-label extension; PK = Pharmacokinetic; QoL = Quality of life; QOLIE-31 = Quality of Life in Epilepsy Inventory-31; TC = Telephone Call; Tx = Treatment.

Table 1b. Schedule of Assessments for Patients Continuing in the OLE

Study Period	Open-label Treatment													Post-Tx Follow-up ^{F,G}			
Visit Number	8A*	9	10	11	12	13A	14A-TC ^I	15A ^I	16-TC	17	18-TC	19	20-TC	21	F1b	F2b	ET
Study Day	56±3	77±3	161±7	245±7	329±7	420±7	511±7	602±7	693±7	784±7	875±7	966±7	1057±7	1148±7	1155±3	1190±10	

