2 INTRODUCTION

2.1 STUDY RATIONALE

XEN1101 is a novel, small molecule, selective KCNQ2/3 ($K_v7.2/7.3$) potassium channel positive allosteric modulator being developed for the treatment of partial-onset (focal) epilepsy. Enhancing the open state of KCNQ2/3 in neurons favors a hyperpolarized resting state, which reduces rapid action potential spiking. **CCI**

XEN1101 was investigated at single doses of 5, 15, 20, 25, and 30 mg, as well as multiple doses of 15 or 25 mg once daily (QD) for up to 10 days in healthy volunteers. The influence of single doses was also investigated for effects on cortical and corticospinal excitability using transcranial magnetic stimulation (TMS) techniques. XEN1101 was well tolerated, adverse events (AEs) were generally transient, dose/exposure related, and the majority of AEs were mild. The most common related AEs were central nervous system (CNS) effects such as dizziness and sedation, consistent with this class of drugs (antiepileptics). The pharmacokinetics (PK) of XEN1101 were found to be suitable for QD dosing, with absorption of the drug enhanced by food. The terminal elimination half-life was approximately 1 week after repeat dosing in healthy volunteers. The results from the TMS studies in healthy volunteers suggest that the plasma levels expected at the dose regimens to be used in this study are anticipated to decrease cortical excitability and may suppress seizures in epilepsy patients. For detailed summaries of the results of these studies, please see the Investigator's Brochure.

The purpose of this Phase 2 clinical trial is to evaluate the safety, tolerability, and efficacy of XEN1101 as adjunctive therapy in adults with focal-onset epilepsy. For this study, plasma levels expected at the doses chosen were shown to be well tolerated in the first-in-human (FIH) study (XPF-008-101a) and pharmacologically active in the brain in the companion TMS crossover study (XPF-008-101b).

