- Physical and neurologic examinations, including ophthalmoscopy.
- Vital signs.
- 12-lead ECG.
- Concomitant medications, including any changes to AEDs.
- Site check of eDiary compliance.
- Clinical laboratory tests.
- Blood sample for PK analysis (XEN1101).
- CCI

Visit F2a – Study Day 98 (42 ± 7 days post last dose) in patients NOT entering the OLE

Upon completion of Visit F2a (or the ET visit, when applicable), the patient's participation in the study will be finished. The following assessments should be completed at Visit F2a:

- C-SSRS.
- AEs.
- Physical and neurologic examinations, including ophthalmoscopy.
- Vital signs.
- Weight and BMI.
- 12-lead ECG.
- AUA Symptom Index.
- QoL assessment (QOLIE-31).
- CGI.
- PGI-C.
- Concomitant medications, including any changes to AEDs.
- Site check of eDiary compliance.
- Urine pregnancy test for females of childbearing potential (if positive a serum pregnancy test will be performed).

- Clinical laboratory tests.
- Blood sample for PK analysis (XEN1101).
- Return of eDiary device.

Unscheduled Visit(s)

Patients may return to the site between scheduled study visits as required for safety management, eDiary re-training/maintenance or for other reasons. The investigator will determine the tests and procedures to be performed at an unscheduled visit, which should be recorded in the source and eCRF.

Early Termination (when applicable)

If the patient discontinues or is withdrawn from the study, and is unwilling or unable to complete the follow up visits (F1a and F2a), efforts should be made to complete the ET evaluations and report the observations up to the time of withdrawal as thoroughly as possible. The following assessments should be performed on the last day the patient was treated with the IMP or as soon as possible thereafter:

- C-SSRS.
- AEs.
- Physical and neurologic examinations, including ophthalmoscopy.
- Vital signs.
- Weight and BMI.
- 12-lead ECG.
- AUA Symptom Index.
- QoL assessment (QOLIE-31).
- CGI.
- PGI-C.
- Concomitant medications, including any changes to AEDs.
- Site check of eDiary and IMP compliance.
- Urine pregnancy test for females of childbearing potential (if positive a serum pregnancy test will be performed).
- Clinical laboratory tests.
- Blood collection for biomarker assessment (not mandatory for inclusion in the study).
- Blood sample for PK analysis (XEN1101).
- Collect remaining IMP supply from patient.
- Return of eDiary device.
- CCI

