Patients in whom XEN1101 dosing has been stopped for any reason will be required to complete a site visit one week (7 ± 3 days) following their last dose of XEN1101 (following Visit F1b procedures) and to complete a follow-up visit 42 ± 10 days following their last dose (following Visit F2b procedures). Patients will be requested to continue completing their diary until the last study visit. Refer to [Table 1b Schedule of Assessments](#).

Patients who discontinue early from the study and are unwilling or unable to complete the follow up visits (F1b and F2b) should have all ET evaluations performed on the last day of receiving the XEN1101, or as soon as possible thereafter.

Visit F1b – Study Day 1155 (7 ± 3 days post last OLE dose)

- C-SSRS.
- AEs.
- Physical and neurologic examinations, including ophthalmoscopy.
- Vital signs.
- 12-lead ECG.
- Concomitant medications, including any changes to AEDs.
- Collect and check used diary and resupply of new paper diary.
- Clinical laboratory tests.
- CCI

Visit F2b – Study Day 1190 (42 ± 10 days post last OLE dose)

Upon completion of Visit F2b (or the ET visit, when applicable), the patient's participation in the study will be finished. The following assessments should be completed at Visit F2b:

- C-SSRS.
- AEs.
- Physical and neurologic examinations, including ophthalmoscopy.
- Vital signs.
- Weight and BMI.
- 12-lead ECG.
- AUA Symptom Index.
- QoL assessment (QOLIE-31).
- CGI-S.
- PGI-S.
- Concomitant medications, including any changes to AEDs.
- Urine pregnancy test for females of childbearing potential (if positive a serum pregnancy test will be performed).
- Clinical laboratory tests.
- Return of paper diary.

Unscheduled Visit(s)

Patients may return to the site between scheduled study visits during the OLE as required for safety management, diary re-training or for other reasons. The investigator will determine the tests and procedures to be performed at an unscheduled visit, which should be recorded in the source and eCRF.

Early Termination (when applicable)

If the patient discontinues or is withdrawn from the OLE phase of the study, and is unwilling or unable to complete the follow-up visits (F1b and F2b), efforts should be made to complete the ET evaluations and report the observations up to the time of withdrawal as thoroughly as possible. The following assessments should be performed on the last day the patient was treated with the study drug, or as soon as possible thereafter:

- C-SSRS.

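### For patients who leave by the early termination route, participation ends up to 42 days before the adverse event recording window closes, and no later contact is scheduled.

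*Combined protocol and SAP*

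**What the plan says.** **The recording window.** Section 8.4.4.1: "All AEs occurring from screening (after signing of the ICF) until 42 days following the last administration of IMP must be recorded".

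**When participation ends.** Section 8.1, double-blind period (DBP): "Upon completion of Visit F2a (or the ET visit, when applicable), the patient's participation in the study will be finished". The open-label extension (OLE) text has the same construction: "Upon completion of Visit F2b (or the ET visit, when applicable", with the same consequence.

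**Who has an ET visit, according to the body text.** Section 8.1 opens the DBP instruction with "If the patient discontinues or is withdrawn from the study, and is unwilling or unable to complete the follow up visits (F1a and F2a". The OLE text in Section 8.1 and the Note in Section 7.3 carry the same condition, as does the DBP part of Section 6.1.2. Read this way, ET is a fallback.

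**Who has an ET visit, according to the schedule.** Table 1a note L reads, up to its closing words: "Patients who discontinue early from the study should have all ET evaluations performed on the last day of receiving study drug, or as soon as". Neither this note, nor Table 1b note G, nor the last sentence of Section 7.3 carries the condition about being willing and able to attend follow-up.

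**The default follow-up.** Sections 7.2 and 8.1, Table 1a note K and Table 1b note F require patients whose dosing has stopped to attend F1 at 7 ± 3 days and F2 at 42 ± 7 days (F2a) or 42 ± 10 days (F2b) after the last dose. Section 6.1.2 repeats this for the DBP. AEs are collected at both visits.

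**Half-life.** Section 2.1: "The terminal elimination half-life was approximately 1 week after repeat dosing in healthy volunteers".

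**The concern.** A mandatory recording window needs a contact at or after its end. For patients on the ET route there is none: their last contact can fall on the final dosing day, and Section 8.1 then closes their participation. Section 8.4.4 describes AE reporting in terms of what is detected or volunteered at visits, so with no visit there is no planned way to learn of a new event.

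Safety in the DBP, including suicide risk on the C-SSRS, is a primary objective (Section 3). With a half-life of about a week, most of the drug is still present at an ET visit held on time, so the unobserved weeks are those in which drug-related and withdrawal-related events could still appear. The conflict between the schedule notes and the body text adds to this. A site working from the tables could close AE collection at ET for a patient who would have accepted F1 and F2.

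**Working it through.** **1. The plan's own figure.** The 42-day window matches the nominal final visits:
- DBP: F2a on Day 98, last dose on Day 56; 98 − 56 = 42.
- OLE: F2b on Day 1190, last dose on Day 1148; 1190 − 1148 = 42.

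The window and the default schedule therefore agree. The gap comes from the ET route and, to a smaller extent, from the visit tolerances.

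**2. Days of the window after the last scheduled contact.** Uncovered days = 42 − (day of last contact after the last dose). The earliest F2a is at 42 − 7 = 35 days and the earliest F2b at 42 − 10 = 32 days. An ET delayed to day 7 is an assumption, included for illustration. Drug remaining = 0.5^(day/7), which assumes simple exponential decay at the healthy-volunteer half-life of about 7 days. On that figure, 42 days is 42/7 = 6 half-lives.

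| Last scheduled contact | Day after last dose | Uncovered days | Share of 42 | Drug remaining |
|---|---|---|---|---|
| F2a or F2b at nominal day | 42 | 0 | 0% | 1.6% |
| F2a at earliest | 35 | 7 | 17% | 3.1% |
| F2b at earliest | 32 | 10 | 24% | 4.2% |
| ET delayed to day 7 (assumed) | 7 | 35 | 83% | 50% |
| ET on last dosing day | 0 | 42 | 100% | 100% |

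The last column gives context only. It does not measure how many events are missed.

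**3. Who is sent to ET.** The texts give different answers for a patient who leaves the study early but would attend follow-up:
- Sections 6.1.2 (DBP), 7.3 (Note) and 8.1: no ET visit, because ET is only for those who will not or cannot attend F1 and F2.
- Table 1a note L, Table 1b note G and the last sentence of Section 7.3: an ET visit at or soon after the last dose.

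The OLE gives a concrete case. Under Section 6.1.2, a patient with continuing intolerance stops drug and is withdrawn from the study. Section 7.2 and note F then call for F1b and F2b. Note G calls for ET, and Section 8.1 treats participation as finished once ET is complete. The same patient has AE contact to about day 42 under one reading and possibly none after the last dose under the other.

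**4. What still operates after ET.** Section 7.2 has patients told to call at once about any serious adverse event (SAE) or other event of significant concern to them. Section 8.4.4 has the investigator follow AEs, and events that led to discontinuation, until they resolve or are explained. The first is passive; the second concerns events already known. Neither asks the patient about new events.

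**The case against.** The strongest reply is that the protocol already covers early stopping. Anyone whose drug is stopped for any reason is required to attend F1 and F2, and F2 is nominally at day 42. On the body text, ET is left for those who leave and also decline or cannot attend, some of whom will have withdrawn consent, so that no wording would recover their data. This largely stands. A reader might infer that all early leavers lose the window, and the documents do not support that. The reply does not remove the conflict with notes L and G and the end of Section 7.3, and patients unable to travel may still be reachable by telephone.

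Second, collection after ET is not nil. Patients are told to call about serious events, known events are followed, detailed SAE procedures sit in the Study Operations Manual, and pregnancy reporting runs for 6 months after the last dose without a visit attached. This stands too. What is missing is scheduled questioning about new events, not every reporting route.

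Third, ET may take place later than the last dosing day, so 42 uncovered days is the extreme. That is correct, and the size is stated as a maximum.

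Fourth, a symmetric visit window is an ordinary scheduling tolerance. That is fair, and the 7- or 10-day shortfall is secondary. But Section 8.1 ends participation at that visit, so an early F2 still leaves the mandatory window open.

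Fifth, a reader might infer biased arm comparisons. That cannot apply to the OLE, where all patients are assigned 20 mg and there is no placebo arm. In the DBP it is plausible, because Section 2.3.1 reports more moderate CNS events with repeat dosing at 25 mg once daily, but the documents do not show that ET exits would differ by arm, and the DBP safety analysis is descriptive (Section 9.4.4).

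**Conclusion.** The point holds for patients on the ET route. As written, Section 8.1 can end their participation up to 42 days before the recording window in Section 8.4.4.1 closes, with no scheduled means of learning of new AEs in between. The schedule notes and the last sentence of Section 7.3 widen the affected group beyond what the body text intends. For patients on the default route the shortfall is 0 days at the nominal visit and at most 7 days (DBP) or 10 days (OLE) at the earliest permitted one.

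The 42-day maximum assumes ET on the last dosing day; any delay shortens it day for day. The drug-remaining figures assume a 7-day half-life and simple decay. The protocol gives no rate or count of ET visits, so the number of patients affected cannot be derived. Differential under-counting between DBP arms is a possibility to check, not a finding.

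**What to change.** 1. **Reconcile the ET wording.** Bring Table 1a note L, Table 1b note G and the last sentence of Section 7.3 into line with the condition in Sections 6.1.2, 7.3 (Note) and 8.1, so that F1 and F2 are the default follow-up and ET the fallback.
2. **Separate the end of visits from the end of AE collection.** In Section 8.1, for both DBP and OLE, state that ET ends site visits but not AE collection. Unless the patient refuses contact, add one telephone call on or after day 42 from the last dose, covering AEs and SAEs, concomitant medications and the C-SSRS. Visits 4 and 7 already collect these by telephone. Make the same call where F2a or F2b falls before day 42.
3. **Report completeness.** Tabulate by DBP arm how many patients had AE collection to day 42, so that any imbalance is visible when the safety tables are read.

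The cost is revised wording, one call per affected patient and one extra table. Some patients will refuse the call, and for them the gap remains; the table will show how many had no coverage to day 42.
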